In elderly patients, in patients with advanced liver disease or in patients with debilitating disease, the usual starting dose is 0.25 mg, given two or three times daily. This may be gradually increased if needed and tolerated. The elderly may be especially sensitive to the effects of benzodiazepines. If side effects occur at the recommended starting dose, the dose may be lowered.

HOW SUPPLIED

XANAX Tablets are available as follows:

0.25 mg (white, oval, scored, imprinted "XANAX 0.25")	
Bottles of 100	NDC 0009-0029-01
Reverse Numbered	
Unit dose (100)	NDC 0009-0029-46
Bottles of 500	NDC 0009-0029-02
Bottles of 1000	NDC 0009-0029-14
0.5 mg (peach, oval, scored, imprinted "XANAX 0.5")	
Bottles of 100	NDC 0009-0055-01
Reverse Numbered	
Unit Dose (100)	NDC 0009-0055-46
Bottles of 500	NDC 0009-0055-03
Bottles of 1000	NDC 0009-0055-15
1 mg (blue, oval, scored, imprinted "XANAX 1.0")	
Bottles of 100	NDC 0009-0090-01
Bottles of 500	NDC 0009-0090-04
Bottles of 1000	NDC 0009-0090-13
2 mg (white, oblong, multi-scored, imprinted "XANAX" on one side and "2" on the reverse side)	
Bottles of 100	NDC 0009-0094-01
Bottles of 500	NDC 0009-0094-03

[figure not shown]
Store at controlled room temperature 20° to 25°C (68° to 77°F) [see USP].

Rx only

ANIMAL STUDIES

When rats were treated with alprazolam at 3, 10, and 30 mg/kg/day (15 to 150 times the maximum recommended human dose) orally for 2 years, a tendency for a dose related increase in the number of cataracts was observed in females and a tendency for a dose related increase in corneal vascularization was observed in males. These lesions did not appear until after 11 months of treatment.

This product's label may have been updated. For current full prescribing information, please visit www.pfizer.com.

LAB-0004-10.0
 January 2017

MEDICATION GUIDE
XANAX (ZAN-aks)
(alprazolam) Tablets, C-IV

What is the most important information I should know about XANAX?

- **XANAX is a benzodiazepine medicine. Taking benzodiazepines with opioid medicines, alcohol, or other central nervous system depressants (including street drugs) can cause severe drowsiness, breathing problems (respiratory depression), coma and death.**
- **XANAX can make you sleepy or dizzy, and can slow your thinking and motor skills.**
 - Do not drive, operate heavy machinery, or do other dangerous activities until you know how XANAX affects you.
 - Do not drink alcohol or take other drugs that may make you sleepy or dizzy while taking XANAX without first talking to your healthcare provider. When taken with alcohol or drugs that cause sleepiness or dizziness, XANAX may make your sleepiness or dizziness much worse.
- Do not take more Xanax than prescribed.

What is XANAX?

- XANAX is a prescription medicine used:
 - to treat anxiety disorders
 - for the short-term relief of the symptoms of anxiety
 - to treat panic disorder with or without a fear of places and situations that might cause panic, helplessness, or embarrassment (agoraphobia)
- **XANAX is a federal controlled substance (C-IV) because it can be abused or lead to dependence.** Keep XANAX in a safe place to prevent misuse and abuse. Selling or giving away XANAX may harm others, and is against the law. Tell your healthcare provider if you have abused or been dependent on alcohol, prescription medicines or street drugs.
- It is not known if XANAX is safe and effective in children.
- Elderly patients are especially susceptible to dose related adverse effects when taking XANAX.
- It is not known if XANAX is safe and effective when used to treat anxiety disorder for longer than 4 months.
- It is not known if XANAX is safe and effective when used to treat panic disorder for longer than 10 weeks.

Do not take XANAX if:

- you are allergic to alprazolam, other benzodiazepines, or any of the ingredients in XANAX. See the end of this Medication Guide for a complete list of ingredients in XANAX.
- you are taking antifungal medicines including ketoconazole and itraconazole

Before you take XANAX, tell your healthcare provider about all of your medical conditions, including if you:

- have or have had depression, mood problems, or suicidal thoughts or behavior
- have liver or kidney problems
- have lung disease or breathing problems
- are pregnant or plan to become pregnant. XANAX may harm your unborn baby. You and your healthcare provider should decide if you should take XANAX while you are pregnant.
- are breastfeeding or plan to breastfeed. XANAX passes into your breast milk and may harm your baby. Talk to your healthcare provider about the best way to feed your baby if you take XANAX. You should not breastfeed while taking XANAX.

Tell your healthcare provider about all the medicines you take, including prescription and over-the-counter medicines, vitamins, and herbal supplements.

Taking XANAX with certain other medicines can cause side effects or affect how well XANAX or the other medicines work. Do not start or stop other medicines without talking to your healthcare provider.

How should I take XANAX?

- See "**What is the most important information I should know about XANAX?**"
- Take XANAX exactly as your healthcare provider tells you to take it. Your healthcare provider will tell you how much XANAX to take and when to take it.
- If you take too much XANAX, call your healthcare provider or go to the nearest hospital emergency room right away.

MEDICATION GUIDE
XANAX (ZAN-aks)
(alprazolam) Tablets, C-IV

What should I avoid while taking XANAX?

- XANAX can cause you to be drowsy. Do not drive a car or operate heavy machinery until you know how XANAX affects you.
- You should not drink alcohol while taking XANAX. Drinking alcohol can increase your chances of having serious side effects.

What are the possible side effects of XANAX?**XANAX may cause serious side effects, including:**

- See "**What is the most important information I should know about XANAX?**"
- **Abuse and dependence.** Taking XANAX can cause physical and psychological dependence. Physical and psychological dependence is not the same as drug addiction. Your healthcare provider can tell you more about the differences between physical and psychological dependence and drug addiction.
- **Withdrawal symptoms.** You may have withdrawal symptoms if you stop taking XANAX suddenly. Withdrawal symptoms can be serious and include seizures. Mild withdrawal symptoms include a depressed mood and trouble sleeping. Talk to your healthcare provider about slowly stopping XANAX to avoid withdrawal symptoms.
- **Seizures.** Stopping XANAX can cause seizures and seizures that will not stop (status epilepticus).
- **Mania.** XANAX may cause an increase in activity and talking (hypomania and mania) in people who have depression.

The most common side effects of XANAX include drowsiness and light-headedness. These are not all the possible side effects of XANAX. Call your doctor for medical advice about side effects. You may report side effects to FDA at [name].

How should I store XANAX?

- Store XANAX between 68°F to 77°F 20°C to 25°C
- **Keep XANAX and all medicines out of the reach of children.**

General information about the safe and effective use of XANAX.

- Medicines are sometimes prescribed for purposes other than those listed in a Medication Guide.
- Do not use XANAX for a condition for which it was not prescribed.
- Do not give XANAX to other people, even if they have the same symptoms that you have. It may harm them.
- You can ask your pharmacist or healthcare provider for information about XANAX that is written for health professionals.

What are the ingredients in XANAX?

[figure not shown]
Active ingredient: alprazolam

Inactive ingredients: Cellulose, corn starch, docusate sodium, lactose, magnesium stearate, silicon dioxide and sodium benzoate. In addition, the 0.5 mg tablet contains FD&C Yellow No. 6 and the 1 mg tablet contains FD&C Blue No. 2.

XANAX® is a registered trademark of Pharmacia & Upjohn Company LLC. For more information, go to www.pfizer.com or call [name].

This Medication Guide has been approved by the U.S. Food and Drug Administration.

This product's label may have been updated. For current full prescribing information, please visit www.pfizer.com.

LAB 0825-1.0
December 2016

Revised: 1/2017

Pharmacia and Upjohn Company LLC

## LIST OF ABBREVIATIONS

AE	adverse events
AED	antiepileptic drugs
ATC	anatomical-therapeutic-chemical
AUCinf	area under the concentration curve from 0 to infinity
AUClast	area under the concentration curve from 0 to the last measurable value
CI	confidence interval
Cmax	maximum concentration
CRU	clinical research unit
CTCAE	Common Terminology Criteria for Adverse Events
EMU	epilepsy monitoring unit
FDA	Food and Drug Administration
ITT	intend-to-treat
ICH	International Committee for Harmonization
MedDRA	Medical Dictionary for Drug Regulatory Affairs
PBRS	Peachtree BioResearch Solution
PCS	potentially clinically significant
PD	pharmacodynamic
PK	pharmacokinetic
PI	principal investigator
PP	per-protocol
SAE	serious adverse events
SAP	statistical analysis plan
SAS	statistical analysis system
SD	standard deviation
SOC	system organ class
Tmax	time to maximum
US	United States
VAS	visual analog scale
WHODRUG	World Health Organization Drug Dictionary

## 1. INTRODUCTION

### 1.1 Objectives

The overall objectives of the study are to assess the efficacy and safety of a single administration of STAP-001 in subjects with epilepsy with a predictable seizure pattern.

The primary objectives are:

- To assess the efficacy of STAP-001 (1.0 mg and 2.0 mg) compared to placebo in treating a seizure episode
- To assess the clinical feasibility and safety of the inhalation of STAP-001 (1.0 mg and 2.0 mg) compared to placebo in subjects during a seizure episode
- To assess the sedation associated with administration of STAP-001 (1.0 mg and 2.0 mg) compared to placebo

### 1.2 Design

This is a multicenter, dose-ranging study to investigate the efficacy, safety, and clinical usability of STAP-001 in adult (18 years of age and older) subjects with epilepsy with a predictable seizure pattern.

This is an in-patient study. Eligible and qualified subjects will be admitted to a Clinical Research Unit (CRU) or Epilepsy Monitoring Unit (EMU) for study participation. The duration of the stay in the in-patient unit during the Treatment phase will be 2-8 days. The study consists of two parts: Part 1- Open-Label Feasibility; Part 2 - Double-Blind.

#### 1.2.1 Part 1: Open-Label Feasibility

The first subjects enrolled in the study will participate in an open-label feasibility evaluation. Enrollment in this phase will end when there are data from at least 8 individual subjects with a treated single seizure episode in a CRU/EMU. Eligible subjects will receive a single dose of 1 mg STAP-001 at the onset of their predictable seizure episode. The subjects will undergo all study procedures and evaluations as outlined in this protocol. The feasibility data (with special emphasis on the drug administration and clinical assessment procedures) from these 8 subjects will be analyzed and reviewed by the Sponsor before starting the double-blind part of the study. If deemed necessary based on the feasibility data, the study protocol will be amended (for example, to change the drug administration procedure or to redefine the time frame for primary endpoint assessment), before starting the double-blind part of the study.

#### 1.2.2 Part 2: Double-Blind

After admission to the in-patient unit eligible and qualified subjects will be stratified by the use of inducing vs non-inducing AED and the use of chronic daily benzodiazepines (yes or no) and randomly assigned (1:1:1) to one of two doses of STAP-001 (1 mg or 2 mg) or Staccato placebo. A blood sample for PK analysis (pre-dose) will be obtained. For each subject, a single seizure episode will be treated and assessed. Study medication will be self-administered (when feasible) or administered by a Staff Caregiver when a predictable seizure episode starts. Assessment of the seizure activity is based on clinical observation by the Staff Caregiver using a stop watch. In addition, a video EEG will record the occurrence, start time, and duration, of the seizure event. PK samples will be collected 10, 30 and 60

minutes, and 2 and 6 hours after the administration of the study drug. If possible, subjects will signal when they experience a seizure event. Subject will be under video EEG surveillance throughout the Treatment Phase. The Staff Caregiver will signal the event for the video EEG recording, starts the stop watch at the time of drug administration, and mark the occurrence of the seizure event on a seizure diary. If the seizure episode does not stop within 5 minutes of the study drug administration, rescue medication other than alprazolam may be administered at the discretion of the principal investigator per the protocol of the research unit. The study exit procedures will be conducted 24 to 32 hours after the administration of study medication or when the subject discontinues from the study.

After discharge from the in-patient unit there will be a safety-follow-up phone contact  $14 \pm 2$  days after the subject received the study medication.

## 2. ELABORATION OF STUDY PROTOCOL

### 2.1 Study Populations

Five analysis populations will be defined and analyzed:

1. The Efficacy Population (ITT population) will include all subjects who have a seizure event and receive study drug during the Treatment Period.
2. Modified Intent to Treat (mITT) population will consist of all subjects who have a seizure event, receive study drug, and have had at least one evaluation after study drug administration. mITT will be used for primary efficacy analysis.
3. The Per Protocol Population will include all subjects in the Efficacy Population who were dosed according to protocol and have no major protocol deviations. Major protocol deviations will be identified by Engage Therapeutics, Inc., before the database is locked and unblinded.
4. The PK Population will include all subjects who receive study drug and have at least one pharmacokinetic data point during the Treatment Period. Subjects who receive placebo will be excluded from the PK Population. PK concentrations will be analyzed using PK population.
5. The Safety Population will include all subjects who receive study drug during the Treatment Period from both Part 1 Open-label Feasibility and Part 2 Double-blind. All safety parameters will be analyzed using safety population.

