### 3.6 Key Data Items

#### Study Analysis Population Definition:

- Intend-To-Treat (ITT) population: All subjects who have seizure events and received study drug.
- Modified Intend-to-Treat (mITT) population: All ITT subjects have had at least one efficacy evaluation after study drug dosed
- Per-Protocol (PP) population: All ITT subjects without any major protocol deviations.
- PK Population: All ITT subjects who provided at least one PK data point.
- Safety Population: All ITT subjects who receive at least one dose of study drug.

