## 4. OUTPUT PLANNED FOR THE STUDY REPORT (BLINDED PHASE)

### 4.1 Tables to be Included in Study Report

In the following sections, the different results are presented in the order in which it is planned to make them appear in the study report.

The table templates are available in the Appendix of the SAP. The content shown in the templates does only mean as an example. It is not based on real study data or details concerning design.

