#### **4.1.4 Summary of Safety Endpoints**

Table 14.3.1.1 Summary of Adverse Events – Safety Set

Table 14.3.1.2 Summary of Adverse Events by MedDRA System Organ Class and Preferred Term – Safety Set

Table 14.3.1.3 Summary of Serious Adverse Events by MedDRA System Organ Class and Preferred Term – Safety Set

Table 14.3.1.4 Summary of Adverse Events by Severity, MedDRA System Organ Class and Preferred Term – Safety Set

Table 14.3.1.5 Summary of Adverse Events by Relationship to Study Agent, MedDRA System Organ Class and Preferred Term – Safety Set

Table 14.3.1.6 Summary of Adverse Events by MedDRA Preferred Term and Overall Frequency – Safety Set

Table 14.3.2.1 Summary of Vital Signs by Time Point – Safety Set

Table 14.3.2.2 Summary of Vital Signs Change from Baseline by Time Point – Safety Set

Table 14.3.3.1 Summary of ECG by Time Point – Safety Set

Table 14.3.3.2 Summary of ECG Change from Baseline by Time Point – Safety Set

Table 14.3.3.3 Summary of ECG Category Results by Time Point – Safety Set

Table 14.3.3.4 Summary of ECG Interpretation by Category and Time Point – Safety Set

Table 14.3.4.1 Summary of Physical Examination by Visit – Safety Set

Table 14.3.4.2 Summary of Neurological Examination by Visit – Safety Set

Table 14.3.5.1 Summary of Laboratory (Hematology) Test Results – Safety Set

Table 14.3.5.2 Summary of Laboratory (Blood Chemistry) Test Results – Safety Set

Table 14.3.5.3 Summary of Laboratory (Urine) Continuous Test Results – Safety Set

Table 14.3.5.4 Summary of Laboratory (Urine) Category Test Results – Safety Set

Table 14.3.5.5 Number and Percentage Subjects with TEPCS Laboratory (Hematology) Test Results – Safety Set

Table 14.3.5.6 Number and Percentage Subjects with TEPCS Laboratory (Blood Chemistry) Test Results – Safety Set

Table 14.3.5.7 Number and Percentage Subjects with TEPCS Laboratory (Urine) Test Results – Safety Set

Table 14.3.5.8 Number and Percentage Subjects with Abnormal Laboratory (Hematology) Test Results – Safety Set

Table 14.3.5.9 Number and Percentage Subjects with Abnormal Laboratory (Blood Chemistry) Test Results – Safety Set

Table 14.3.5.10 Number and Percentage Subjects with Abnormal Laboratory (Urine) Continuous Test Results – Safety Set

Table 14.3.6.1 Summary of Sedation and Alert Scale VAS – Safety Set

Table 14.3.6.2 Summary of Sleepy and Awake Scale VAS – Safety Set

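### As written, the SAP would put open-label Part 1 subjects in the same 1 mg column as randomised subjects in the safety and sedation tables, and its passages on scope do not agree

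*SAP*

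**What the plan says.** **Who is in the set.** SAP 2.1: "The Safety Population will include all subjects who receive study drug during the Treatment Period from both Part 1". The sentence goes on to name Part 2, so the set is drawn "from both Part 1 Open-label Feasibility and Part 2 Double-blind", and Protocol 13.3.1 does the same. SAP 2.1 adds: "All safety parameters will be analyzed using safety population".

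**What Part 1 is.** SAP 1.2.1: "Eligible subjects will receive a single dose of 1 mg STAP-001 at the onset of their predictable seizure episode". It is open-label and has no placebo group.

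**How tables are split.** SAP 3.1 presents safety data by treatment group and time point. SAP 3.3.3 groups subjects by the drug they received and makes all safety summaries descriptive. The protocol synopsis groups by treatment and dose level. None of these mentions the study part.

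**What the tables serve.** One primary objective in SAP 1.1 is "To assess the sedation associated with administration of STAP-001 (1.0 mg and 2.0 mg) compared to placebo"; safety against placebo is another. The sedation outputs in SAP 4.1.4, such as "Table 14.3.6.1 Summary of Sedation and Alert Scale VAS", are specified on the Safety Set.

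**What points elsewhere.** The SAP section 4 heading, which covers all these tables, begins "OUTPUT PLANNED FOR THE STUDY REPORT (BLINDED PHASE". SAP 3.6 defines the set a second time: "Safety Population: All ITT subjects who receive at least one dose of study drug", with no mention of parts.

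**The concern.** A programmer who applies the population rule and the grouping rule as written has one place to put a Part 1 subject: the 1 mg column. The documents give several reasons why Part 1 may differ from the randomised 1 mg arm:

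- Subjects knew they had active drug, and the sedation scale is self-rated (Protocol 11.7).
- They were enrolled first, at 3 to 8 sites with at most three per site (Protocol section 7, Part 1), against about 50 sites overall (Protocol 7.1).
- They were not stratified. Part 2 stratifies on enzyme-inducing antiepileptic drugs and chronic daily benzodiazepines. Adding unstratified subjects to one arm can disturb that balance.
- Drug administration procedures could be amended between the parts (SAP 1.2.1).
- Protocol 7.3.1 reports low plasma alprazolam in the first subjects dosed, and says that sedation has followed peak plasma levels.

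At stake is the clean reading of 1 mg against placebo for sedation and safety. The descriptive columns are the only planned analysis of those objectives, and the visible SAP text specifies no Part 2-only safety table as a check.

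**Working it through.** **1. The plan's own sample size (SAP 2.3), as background.** Inputs: 57% versus 20% responders, two-sided 0.05, 90% power. With pooled variance and no continuity correction:

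n = [1.960·√(2·0.385·0.615) + 1.282·√(0.57·0.43 + 0.20·0.80)]² / 0.37² ≈ (1.349 + 0.816)² / 0.1369 ≈ 34.2, so 35 per arm.

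This reproduces the stated 35. Power at 35 per arm is 90.7%. It concerns efficacy, so the handling of Part 1 in safety tables does not alter it.

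**2. Share of a pooled 1 mg column.** Inputs: Part 1 has about 9 enrolled and at least 8 evaluable (Protocol 7.1). The Part 2 1 mg arm has about 35 evaluable, or at most 115/3 ≈ 38 if everyone enrolled is dosed. Share s = k/(n + k):

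| Part 1 (k) | Part 2 1 mg (n) | Column total | Share |
|---|---|---|---|
| 8 | 35 | 43 | 18.6% |
| 9 | 35 | 44 | 20.5% |
| 8 | 38 | 46 | 17.4% |
| 9 | 38 | 47 | 19.1% |

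The placebo and 2 mg columns contain Part 2 subjects only, under either reading.

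**3. Shift in the 1 mg column.** If Part 1 differs from the randomised 1 mg arm by D, the pooled mean or proportion moves by s × D. The documents do not give D, so these are assumed values, with n = 35:

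| D (mm or percentage points) | k = 8 | k = 9 |
|---|---|---|
| 5 | 0.93 | 1.02 |
| 10 | 1.86 | 2.05 |
| 20 | 3.72 | 4.09 |
| 30 | 5.58 | 6.14 |
| 40 | 7.44 | 8.18 |

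For the visual analogue scale, D of 5 to 30 mm gives 0.9 to 6.1 mm. For adverse event incidence, D of 10 to 40 points gives 1.9 to 8.2 points. With n = 38 the shifts are slightly smaller (10 × 8/46 = 1.7 instead of 1.9).

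**4. The scope passages side by side.**
- SAP 2.1 and Protocol 13.3.1: both parts, explicitly.
- SAP section 4 heading: blinded phase, which on its face means Part 2 only.
- SAP 3.6: a subset of the ITT population. SAP 2.1 does not tie that population to a part, while the protocol synopsis confines the efficacy population to the double-blind period. Depending on which is meant, SAP 3.6 covers both parts or Part 2 alone.

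The first two cannot both hold for a table labelled Safety Set, and the third does not settle it.

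**The case against.** The strongest reply is that SAP 2.1 defines who belongs to a population, not how tables are laid out. No sentence says that Part 1 shares a column with randomised subjects. Layout is set by the table shells, which are attached to the SAP but not in the available text, and their absence cannot be counted as a gap in the plan. The section 4 heading suggests Part 2-only tables, and SAP 3.5 also limits one listing to the blinded phase, so the authors did distinguish the parts. All safety endpoints are also listed by subject. This stands to the extent that merging is an inference. It does not remove the point: the heading conflicts with an explicit definition and does not override it, and none of the visible grouping rules separates the parts.

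A reader might infer that the whole placebo comparison of sedation and safety ceases to be randomised. The documents do not support that, because 2 mg versus placebo stays within Part 2. A reader might also take 1 mg versus 2 mg as the trial's central comparison. The objectives and the pairwise tests set each dose against placebo. No pairwise test between doses is planned, and dose-response is only explored by regression on the primary efficacy endpoint.

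Including Part 1 in the Safety Population is itself legitimate and is stated consistently in both documents. The weakness is the missing split by part.

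**Conclusion.** The point holds in a limited form. The stated rules, applied literally, would make about 17% to 20% of the 1 mg safety column open-label and non-randomised. The SAP elsewhere points to a different scope, so the intention has to be stated.

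The effect is confined to the descriptive 1 mg versus placebo contrast and to any informal reading of 1 mg against 2 mg. Safety is not tested, so no p-value, error rate or power figure changes.

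The size of any shift rests on assumed differences, and its direction is unknown. Knowing that the drug is active could raise reported sedation, while the low early plasma concentrations could mean less of it. That uncertainty is a reason to show Part 1 separately. It is not evidence that a bias exists.

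**What to change.** 1. Reconcile SAP 2.1, SAP 3.6 and the section 4 heading, keeping one definition of the Safety Population and one statement of which parts the planned tables cover.
2. In each safety and sedation table, show placebo, 1 mg and 2 mg from Part 2 only, with Part 1 open-label 1 mg in a separate column.
3. State that safety and sedation comparisons with placebo, and between doses, use the Part 2 columns.
4. Label any pooled 1 mg column as supplementary, for overall exposure.
5. Check that the table shells follow this layout before unblinding.

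The cost is one extra table column and a few lines of SAP text. No safety data are dropped, and sample size and efficacy power are unchanged. This is a free improvement.
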